approximately 10 minutes of meditation daily via a commercially available app (either Calm App or Headspace App, both of which are commercially readily available) and approximately 15 minutes of yoga via the online tutorial. Yoga & use of the meditation app is estimated to take approximately 30 minutes per day. Patients may engage in any other of the 1st Line AUA therapies as well taking over the counter medications (Table 1). Patients will be called weekly to ascertain treatment compliance and monitor their progress. If symptoms are not improving there will be the option to discuss other treatment options (e.g. accelerate to higher lines of therapy based on AUA guidelines) at 6 weeks.

Women assigned to the Standard of Care alone group will receive any 1st Line and 2nd Line treatments (excluding use of the online yoga and meditation app). Patients will also be called weekly to monitor progress and to ensure no treatment effect secondary to phone calls. If symptoms are not improving there will be the option to discuss other treatment options (e.g. accelerate to higher lines of therapy based on AUA guidelines) at 6 weeks. At the termination of the study women in the standard of care group will receive 3 months of Calm App.

At the 6 week follow-up phone call patients will be given the option for escalation of therapy. Patients will be given the opportunity to escalate their treatment for IC/PBS to higher lines of treatments: use of intravesical Botox or use of sacral neuromodulation. We will record any accelerated therapy used by the patient that may be added during study participation.

For participants who have completed the study but treatment escalation data was not properly captured in RedCap surveys, These participants will be notified via email through RedCap to complete this additional survey.

Outcome measures:

GRA: The Global Response Assessment is a validated tool to assess response to treatment. It is comprised of a single question and has been utilized widely in IC/BPS^{xiii}. This will be collected weekly. However, the primary outcome is the 12 week (3 month) result.

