Data Analysis: Between and within group differences will be evaluated using chi-square analysis as deemed appropriate by the statistician involved in study analysis (e.g. Fisher's Exact test for non-normal distributions of categorical variables and T-test for continuous variables). Differences between groups will be evaluated using Chi-square analyses for categorical variables as deemed appropriate by the statistician involved in study analysis (e.g. Fisher's Exact test for non-normal distributions). T-tests will be utilized for continuous variables, with comparison by Mann Whitney U for non-normal distributions. Within-group differences over time will be analyzed using the McNemar's test. If any baseline differences exist between the groups, a regression or multivariable analysis will determine the contribution of these differences to observed differences between groups. As the GRA and O'Leary-Sant will be collected more frequently, we plan to analyze these results with linear mixed models analysis.

Power Analysis: Power analysis was performed based on previously reported means and standard deviation from treatment effect based on GRA. We assumed that 41 patients in each arm (total 82) would be required to find a difference of 30% between group's pain scores (the primary outcome) with 80% power and alpha of 0.05. In order to achieve power we will need a total of 82 patients. Assuming an approximate 20-25% dropout or loss to follow-up rate, we will plan to randomize approximately 60-120 patients.

13. Provisions to Monitor the Data to Ensure the Safety of Subjects

A DSMB will not be monitoring safety of these procedures as the study risks are low. The intervention arm includes mindfulness and yoga, both of which have been shown to be low-risk interventions with minimal adverse events^{xix}. The control group will undergo standard of care treatments. Theoretically, there could be increased muscle soreness noted in patients in yoga treatment arm. There are no documented adverse events with mindfulness practice.

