We will track adverse events when patients bring up these events during the course of the study with their providers or study coordinators. Because neither of the studied treatments are experimental or associated with above average risk, we do not anticipate any serious adverse events; nonetheless, these will be tracked. Participants will have access to a 24/7 phone number to reach research or clinical staff with concerns. All adverse events will be recorded and reported to the study PI.

We do not anticipate any conditions that would trigger a suspension or termination of the research.

14. Withdrawal of Subjects

Participants may withdraw from the study at any time without penalty and will continue to receive the clinical standard of care. A subject may be withdrawn from the study without her consent at the discretion of the physician and study staff if they believe she no longer meets study inclusion criteria or if she meets exclusion criteria, or if they believe that it is not in her best interest to continue study participation i.e., desire to undergo surgical treatment. Investigators may withdraw a subject if the subject is not following the study protocol. If a woman is withdrawn from the study either at her own discretion or that of the research staff, she may continue with conservative or surgical management of her IC/BPS in the usual fashion. We will collect a withdrawal Global Response Assessment to use for her progress and will utilize her data up until the time point that she is withdrawn from the study.

To minimize withdrawal from the study, patients will be randomized after they have had what they feel to have been adequate time to consider whether or not they would like to participate in the study and they provide consent. We will document reasons for withdrawal from the study if the participant willingly provides this information. We will report eligibility criteria not met or reasons for declining participation in the study if the participant willingly provides this information. The withdrawal procedure is clearly documented in the study consent.

15. Data Management/Confidentiality

PROTOCOL TITLE: MYPAICE: Mindfulness and Yoga for Pain with Interstitial Cystitis Evaluation

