As stated above, the data collection, HIPAA and consent forms will be maintained in a locked file cabinet in the Eubank research area. A separate file will be designated for each participant. A key matching study number to subject's name will be stored on a password protected computer on a secure UNM OBGYN department server. In order to further ensure patient confidentiality, the identifying information will be kept separately from the numbered study files in a locked cabinet. The data will be maintained for 5 years after completion of the study and then destroyed.

PROTOCOL TITLE: MYPAICE: Mindfulness and Yoga for Pain with Interstitial Cystitis Evaluation

No specimens will be archived for future use.

17. Risks to Subjects

Risks of enrollment in the study include loss of confidentiality. We will take every measure to try to ensure the security and confidentiality of participants. Participants will be recruited in a private room or in a private location via phone or HIPAA compliant ZOOM and will have ample time to consider whether they want to participate in the study. Also, locked cabinets will be used to protect patient consent information and collected data. The link identifying patients and their study numbers will be also stored on a password protected computer on a secure UNM OBGYN department server.

There are minimal risks with the intervention arm of this RCT (yoga and mindfulness). Yoga therapy is associated with low risks, such as muscle discomfort or strain though this is rare. Emotional discomfort due to the reflective nature of this therapy is also possible. Both treatment randomizations in this study are well established as options for IC/BPS with an excellent safety profile.

Pregnant women will not be included in the study, so there is no risk to embryos/fetuses. Participants will need to have a negative urine pregnancy test in the last 3 months prior to enrollment or have documentation of a hysterectomy or tubal ligation. If they are pregnant, the patient meets exclusion criteria and will be ineligible to participate.

There are no risks to those who are not subjects.

18. Potential Benefits to Subjects

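### Adverse events are captured only when women raise them, although both arms are called weekly: the harms the protocol foresees are likely to be under-counted, and capture may differ between arms

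*Combined protocol and SAP*

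**What the plan says.** The rule is in Section 13 (Provisions to Monitor the Data to Ensure the Safety of Subjects): "We will track adverse events when patients bring up these events during the course of the study", whether to providers or to coordinators. The section adds a second route, "Participants will have access to a 24/7 phone number to reach research or clinical staff with concerns", and says what happens once an event is known: "All adverse events will be recorded and reported to the study PI". Serious events are not expected but will be tracked. There is no DSMB, and Section 7 states that there are no safety endpoints.

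The protocol names the harms it can foresee. Section 13 says of the intervention that "there could be increased muscle soreness noted in patients in yoga treatment arm". Section 17 (Risks to Subjects) lists muscle discomfort or strain, which it calls rare, and adds: "Emotional discomfort due to the reflective nature of this therapy is also possible".

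Both arms are telephoned every week. Section 12 (Interventions) says of the yoga and mindfulness arm: "Patients will be called weekly to ascertain treatment compliance and monitor their progress". Of the standard-care arm it says: "Patients will also be called weekly to monitor progress and to ensure no treatment effect secondary to phone calls". The table in Section 21 counts 11 weekly calls per participant.

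**The concern.** Both routes to an adverse-event record depend on the woman deciding to mention the event. The statement that all events are recorded governs handling after a report; it does not make anyone ask. Minor strain, or distress that passes within days, is the kind of event people often do not volunteer, and these are the two harms the protocol names. The yoga is done at home from a video, without a DSMB or a safety endpoint, so adverse-event reporting is the main way such harms would come to light.

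Two things are at stake. During the trial, a harm from home practice could go unremarked. Afterwards, any statement that the programme was low risk, or that the arms had similar or different event counts, would rest on reports that nobody solicited. The second is sharper in an unmasked trial in which the two sets of calls are described as having different purposes.

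**Working it through.** The documents give no adverse-event rate, capture rate or safety power, so there is no stated figure to reproduce. The check has three parts.

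**1. Is there any active route?** These are the places where an event could surface:

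- Section 13, providers and coordinators: patient-initiated.
- Section 13, phone line: patient-initiated.
- Section 12, weekly calls: compliance and progress in one arm; progress and equal contact in the other. Harms are not mentioned for either.
- Section 1.3, optional weekly response: about how treatment is going, and intended for qualitative analysis.
- Section 12, outcome measures: PROMIS-PI weekly; HADS at baseline and 12 weeks. These are efficacy measures. HADS would miss distress that arises and resolves between its two time points.
- Section 14, withdrawal: reasons are documented only if the participant offers them.

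No section sets out an adverse-event question, checklist, recall window or grading. The word "only" is the reviewer's summary of this list, because the protocol describes no other route.

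**2. How much could be missed?** The scale is 47 women per group (Section 5.3). Two inputs are assumptions with no source in the documents: a true rate p of 10-20% of yoga-arm women with soreness or strain, and a share c of 20-50% of those events volunteered. One event per woman, independence between women and complete follow-up are also assumed.

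- Women with an event = 47 × p: 47 × 0.10 = 4.7 to 47 × 0.20 = 9.4.
- Expected number recorded = 47 × p × c.
- Chance that none is recorded = (1 − p × c)^47.

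| p | c | Expected recorded | Chance of none |
|---|---|---|---|
| 10% | 20% | 0.94 | 0.98^47 = 39% |
| 10% | 50% | 2.35 | 0.95^47 = 9.0% |
| 20% | 20% | 1.88 | 0.96^47 = 15% |
| 20% | 50% | 4.7 | 0.90^47 = 0.7% |

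For comparison, full capture at p = 10% gives 0.90^47 = 0.7%. If strain is rarer than assumed, say p = 5%, the chance of an empty record is 9.0% with full capture (0.95^47) and 55% with 25% capture (0.9875^47).

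**3. Could capture differ between arms?** Section 3 says masking is not possible, the named harms belong to the intervention, and only that arm's calls are described as covering compliance. If true rates were equal, the recorded risk ratio would equal the ratio of the capture shares: 0.75/0.50 = 1.5, or 0.75/0.25 = 3.0. With the arms exchanged, these become 0.67 and 0.33. The shares are assumptions. They show what a difference would do, not that there is one.

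**The case against.** The strongest reply is that uneven capture has not been shown. Section 12 gives the purposes of the calls, not their questions, and no call script is in the documents. Contact frequency is deliberately equal. Direction is open too: standard-care women may receive second-line oral agents, instillations and manual physical therapy (Table 1), whose side effects may well come up with treating providers, who are a named reporting route. This stands. A reader might infer that soreness will be over-reported in the yoga arm relative to complaints among controls. The documents support only the possibility of a difference.

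The illustration is also open to attack. The assumed 10-20% rate fits poorly with a protocol that calls strain rare, and the 39% is the worst corner of the grid. If compliance calls do draw out mentions of soreness, yoga-arm capture would lie towards the upper end of the assumed share or above it. This stands as well, so the whole range must be shown. A lower true rate does not rescue the passive rule, however: it reduces the harm at stake but makes an empty record more likely and less informative.

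Third, partial safeguards exist: the phone line, tracking of serious events, the optional weekly comment, and the pain and anxiety scales. They soften the point but do not replace an adverse-event question.

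Finally, repeated prompts about strain and distress could colour a weekly self-rated GRA in an unmasked trial, especially if asked first. That is a fair constraint on the remedy and determines the order of questions proposed below.

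**Conclusion.** The point holds as a weakness in harms ascertainment. The described method is patient-initiated, the protocol foresees specific harms, and weekly calls in both arms offer a better method at little cost. Under-counting is likely because reporting is spontaneous. A difference between arms is possible, but its size and direction cannot be derived. On the assumed rates, about 1 to 5 yoga-arm events would be recorded out of roughly 5 to 9, with a 0.7% to 39% chance of recording none; these figures illustrate and do not predict.

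Two stronger readings should be resisted. It would be wrong to say that the trial has a 39% chance of an empty adverse-event table, because that figure belongs to one pair of unsourced inputs. It would also be wrong to say that the efficacy result is compromised: the primary GRA analysis is unaffected, and the protocol plans no between-arm safety comparison.

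**What to change.** In Section 13, replace the passive rule with one scripted, non-leading question about any new or worsening health problem since the last contact. Ask it in the same words at every weekly call in both arms, after the GRA and the other questionnaires are complete. Record each answer in REDCap, including a negative one, so that silence can be told from absence. Keep the existing spontaneous routes alongside it. Report events by arm and state that ascertainment was solicited.

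The cost is one question in calls already being made; no visit or sample-size change is needed. The downside is that more minor events, and more events arising from the underlying bladder condition, will have to be logged.

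While editing, reconcile the statement in Section 13 that mindfulness has no documented adverse events with the possibility of emotional discomfort given in Section 17.

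### Section 14 lets unmasked staff withdraw women for non-adherence or for wanting surgery and uses their data only up to that point, so week-12 GRA values can be missing for reasons tied to arm or outcome

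*Combined protocol and SAP*

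**What the plan says.** Section 14 (Withdrawal of Subjects) gives staff wide discretion: "A subject may be withdrawn from the study without her consent at the discretion of the physician and study staff". One ground is a belief that "it is not in her best interest to continue study participation i.e., desire to undergo surgical treatment". A separate sentence adds that "Investigators may withdraw a subject if the subject is not following the study protocol". On data, the section says "We will collect a withdrawal Global Response Assessment to use for her progress" and that the study "will utilize her data up until the time point that she is withdrawn from the study".

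Section 12, under Outcome measures, has the GRA collected weekly and then says: "However, the primary outcome is the 12 week (3 month) result". Section 5.3 describes the primary outcome as a linear mixed model of GRA over time, and section 7.1 names both the 3-month GRA and the mixed model. Section 3 states that the trial is unmasked.

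The weekly calls are described differently by arm in section 12. For yoga: "Patients will be called weekly to ascertain treatment compliance and monitor their progress". For standard care: "Patients will also be called weekly to monitor progress and to ensure no treatment effect secondary to phone calls".

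The Data Analysis text in section 12 names chi-square, t-tests and related tests, and a linear mixed model for GRA and O'Leary-Sant. It does not say that women are analysed as randomised, that follow-up continues after withdrawal, or what happens when the week-12 GRA is missing.

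**The concern.** Two of the grounds for withdrawal are not neutral.

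- **Not following the protocol** is tied to arm. Only yoga women have a daily practice to fail at, and only their calls are described as checking compliance.
- **Wanting surgery** is plausibly tied to outcome, because women doing badly are more likely to want it.

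In both cases the decision rests with staff who can know the arm, and use of the woman's data stops before week 12. If non-adherent yoga women leave the comparison, yoga can look better than it is. If poorly responding controls leave, yoga can look worse. The 15% dropout allowance (section 5.3) and the 20-25% allowance (Power Analysis) protect the number of observed women and do nothing about which women are observed.

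**Working it through.** **The plan's own figure.** Inputs from section 5.3: 26% response in controls, a 30-point difference (so 56% with yoga), alpha 0.05 (taken as two-sided), 80% power. With pooled variance and mean rate 0.41:

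n = [1.96 × √(2 × 0.41 × 0.59) + 0.842 × √(0.26 × 0.74 + 0.56 × 0.44)]² / 0.30² = (1.363 + 0.558)² / 0.09 ≈ 41 per arm.

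The dropout step also matches: 41 × 1.15 = 47.15, so 47 per arm. The sample size is not in dispute.

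**Observed rates after withdrawal.** Let w be the share of an arm withdrawn and q the week-12 response those women would have had. The rate among women still observed is (p − w × q) / (1 − w). The values of w and q are my assumptions; the documents give neither.

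| Scenario (true 26% vs 56%) | w | Affected arm reads | Gap reads |
|---|---|---|---|
| Yoga women withdrawn, q = 26% | 5% | (0.56 − 0.05 × 0.26)/0.95 = 57.6% | 31.6 points |
| Same | 10% | (0.56 − 0.10 × 0.26)/0.90 = 59.3% | 33.3 points |
| Same, stress test | 15% | (0.56 − 0.15 × 0.26)/0.85 = 61.3% | 35.3 points |
| Controls withdrawn, q = 0 | 10% | 0.26/0.90 = 28.9% | 27.1 points |
| Same, stress test | 15% | 0.26/0.85 = 30.6% | 25.4 points |
| Withdrawn women respond like their arm | any | unchanged | 30.0 points |

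**No true effect.** Take 26% in both arms, 47 controls observed, and yoga women withdrawn who are all non-responders. Exact rejection rates of an uncorrected chi-square test at two-sided 0.05:

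| w | Yoga n observed | Yoga reads | Rejection | Same n, no selection |
|---|---|---|---|---|
| 5% | 45 | 27.4% | 5.4% | 5.1% |
| 10% | 42 | 28.9% | 6.5% | 5.2% |
| 15% (stress test) | 40 | 30.6% | 7.0% | 4.7% |

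**Mixed model, withdrawal driven by recorded GRA.** Suppose the worst 15% of an arm on weeks 1-6 are withdrawn at week 6, with correlation 0.5 between any two weeks. In simulation, the week-12 mean of the women who stay is off by about 0.18 SD. A likelihood-based model that uses the earlier scores is off by about 0.00 SD.

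**Mixed model, outcome departs from recorded GRA.** Read the stated effect size of 0.85 as SD units, rising linearly to week 12. Withdraw a share w of yoga women at week 6, and assume their true benefit at week 12 is zero. The treatment-policy effect is then 0.85 × (1 − w), and the bias is w × (the week-12 benefit the model implies for them − 0).

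- Benefit tracks the arm to week 6 and is then lost: implied 0.85, so the bias is 0.05 × 0.85 = 0.04, 0.10 × 0.85 = 0.09 and 0.15 × 0.85 = 0.13 SD.
- Never benefited: implied 0.62-0.64 (exchangeable correlation 0.5 or 0.7, or first-order autoregressive 0.9), so the bias is about 0.03, 0.06 and 0.09-0.10 SD.

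The range is therefore 0.03-0.13 SD for 5-15% withdrawn. The upper end needs full benefit to week 6 and complete loss afterwards.

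**The case against.** The strongest reply is that the clause is permissive and may hardly be used. Section 7.3 makes compliance an exploratory endpoint, and routinely removing non-adherent women would defeat it, so the weekly compliance calls may be meant as measurement. The attestation in section 12 asks for daily use only as far as the woman is able, so missed sessions are not clearly a breach. Controls can breach too, by using the study's yoga video or app. The surgery ground looks narrow: women enter on first- and second-line treatment, and escalation from week 6 is recorded as an outcome without ending participation. Weekly GRA in a mixed model, which sections 5.3 and 7.1 put in the primary analysis, also uses everything recorded before withdrawal.

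Most of this stands, and it limits the size of the point. It does not remove it. The clause is the operative rule, and no analysis rule offsets it. The withdrawal GRA is not a week-12 value, and its role in the primary analysis is not stated.

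Three stronger readings are tempting, and the documents do not support them.

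- **That the plan compares adherent yoga women with all controls.** It permits such removals but does not require them.
- **That escalating to a higher line removes a woman.** Section 12 keeps her in and records the therapy. Any dilution from rescue therapy belongs to the treatment-policy effect. Whether sacral neuromodulation counts as surgical is not stated.
- **That the mixed model is biased to the same extent as a completers' comparison.** The simulation shows it is not when withdrawal follows recorded scores.

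**Conclusion.** The point holds as a weakness that should be corrected. Section 14 allows the week-12 GRA to go missing for reasons tied to arm or outcome, and the plan states no as-randomised analysis and no follow-up after withdrawal.

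Under the assumptions shown, withdrawing 5-10% of one arm moves a comparison of observed women by about 2-3 points in the yoga scenario, and 10% moves it by about 3 points the other way in the control scenario. The false-positive rate rises only modestly. The mixed model is exposed mainly where outcome after withdrawal departs from the GRA already recorded.

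A reader might infer that yoga will be overstated, or that the dropout allowances of 15% or 20-25% measure the problem. Neither follows: the direction depends on who is withdrawn, and those are all-cause planning figures, neither estimates of staff withdrawals nor strict limits on them. With no withdrawal rate in the documents, the true impact is unknown. It is nil if withdrawn women respond like the rest of their arm, and may be negligible if the clause is rarely used.

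**What to change.** 1. Amend section 14 so that non-adherence, or wanting or starting a higher line or surgery, ends study treatment at most and never follow-up.
2. Collect the week-12 GRA remotely from every randomised woman who agrees.
3. State that the primary analysis is as randomised, regardless of adherence or escalation, and that the withdrawal GRA does not replace the week-12 value.
4. Report withdrawals by arm, reason and week.

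The cost is a short amendment, matching words in the consent letter if it does not already allow later contact, and one remote call per withdrawn woman: about 2-5 per arm at 5-10% of 47, or 7 at 15%. The sample size of 41 per arm does not change. Some women will decline, so some data will still be missing, and values for women already past week 12 cannot be recovered. Keeping non-adherent yoga women will usually give a smaller contrast than one restricted to adherent women.
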